6.3.6 Secondary Efficacy Analyses

PFS from start of sunitinib according to RECIST 1.1

PFS from start of sunitinib treatment will be derived as date whichever occurred first of any cause of death or date for first tumor progression (which is date for centrally assessed CT performed, according to RECIST 1.1) minus date for start of sunitinib treatment plus 1 day.

For the analysis of PFS only deaths occurring before end-of-trial will be accounted for in the analysis.

Analysis of PFS will be evaluated the following way:

Survival functions will be displayed graphically using Kaplan-Meier plots, and life table statistics will be produced including summaries of number of events and censored observations. Estimates of cumulative 25%, 50% (median) and 75% percentiles of survival with corresponding 95% confidence intervals will be calculated.

Comparison between Intuvax+sunitinib, vs. sunitinib alone will be done using a stratified log-rank test (controlling for strata intermediate/high risk), separate analyses will also be done by strata.

With protocol versions before version 4.0, intermediate risk patients did not have to initiate treatment with sunitinib at a fixed time point according to the visit schedule. Consequently some patients were never started on sunitinib, and in some cases sunitinib treatment was initiated at a later time point. The sunitinib start date constitutes the baseline time point for PFS according to protocol version 4.0 and after. In the analyses, patients who either had a delay or never started sunitinib will be included under the assumption that sunitinib treatment would have been initiated according to the final design, the date of the visit following the nephrectomy visit will be used as baseline.

Another issue that will be considered in the analysis is that some patients may have been discontinued based on general clinical disease progression as evaluated by investigator from symptoms/signs of disease, rather than based on a PD according to RECIST 1.1. For the analysis such cases will be handled strictly based on the RECIST 1.1 evaluation, thus if a patient is withdrawn without a CT confirmed PD the subject will be censored at last CT

Analyses will be based on FAS and repeated for separately by strata..

Proportion of Objective Response Rate (ORR) and Disease Control Rate (DCR) from start of sunitinib

Proportion of ORR from start of sunitinib treatment will be derived as the proportion of patients with the individual's best overall response scored as "CR" or "PR" (using RECIST 1.1) across all time points from first visit six (6) weeks after sunitinib treatment, to end-of-study visit. Similarly, DCR will be derived as proportion of patients with best overall response scored as "CR", "PR" or "SD".

ORR and DCR will be summarised and comparison of treatment groups will be made using the Cochran Mantel-Haenzel test, adjusting for strata.

Duration of response will be derived only for patients meeting the ORR definition CR or PR, at least once, as the date of the first occurrence of PD or death minus the date at which the CR or PR was first observed, plus 1 day. Patients without an occurrence of a PD or death after CR or PR will contribute with the time up till last tumor assessment. Data will be summarised descriptively.

Duration of clinical benefit will be derived only for patients meeting the DCR definition CR, PR or SD at least once, as the date of the first occurrence of PD or death minus the date at which the CR, PR or SD was first observed, plus 1 day. Patients without an occurrence of a PD or death after CR, PR or SD will contribute with the time up till last tumor assessment. Data will be summarised descriptively.

The duration of stable disease is calculated for only those patients who exhibited a best response of stable disease response and will be calculated as the date for the first SD

response to the date of the first observed progression of disease or death before end of trial, if the death was due to disease progression (whichever comes first) plus 1 day. Data will be summarised descriptively.

Response rate from Sunitinib Start Visit

Evaluation of response rate, based on CT and according to the RECIST 1.1 guideline, from Sunitinib Start Visit will be based on the subpopulation from FAS who have been exposed to at least one dose of sunitinib. Number of patients with CR, PR, PD, and SD after start of sunitinib will be summarized using the underlying ordinal scale.

Waterfall charts will be used to display the percent change in target lesion tumour dimension vs best overall response and Two types of Swimmer plots will be created, one with bars showing time from randomization and one from sunitinib start. In these events for progressive disease, end of trial and vital status will be indicated.

Response rate from Screening to Post-Nephrectomy

The evaluation of RECIST response rate between Screening and Post-Nephrectomy assessment will be summarised in the same way as described for response rate after Sunitinib Start Visit.

Time to tumor progression (TTP)

TTP from start of Sunitinib treatment will be derived as date for tumor progression, or clinical disease progression (other than RECIST 1.1) if occurring before tumor progression, minus date for start of sunitinib treatment plus 1 in the same way as done for PFS but excluding any deaths, if death before tumor or disease progression the subject will be censored at time of last CT during the trial. This variable will be analysed using the same method as for the evaluation of PFS.

Infiltrating CD8+ T-cells

The individual evaluation of intratumoral infiltration of CD8+ T-cells will be conducted as described in the protocol, where each patient will have the number of CD8+ T-cells/mm² counted from 3 areas in two separate biopsies by [REDACTED]. Each patients median of the 6 individual counts will be calculated. The patient median number of CD8+ T-cells will be summarised by treatment group, strata and overall using descriptive statistics for continuous data as described in Section 12.1.4.

At the GLP compliant laboratory [REDACTED] a validated automated quantification of intratumoral CD8+ T cells, using whole slide scanning instruments, will be performed. The tumoral area will be delineated by a trained operator and the surface of CD8+ labeling percentage will be assessed in the delineated areas. Each patients mean percentage from the two (2) primary tumor biopsies will be used for statistical evaluations. Patient's mean percentage will be evaluated for the treatment arms per stratum and in total using summary statistics, as described for continuous data in Section 6.3.2.

Relative number of tumor infiltrating CD8+ T-cells in the resected primary tumor compared to number of infiltrating CD8+ T-cells in available diagnostic pre-biopsy (sample from either primary tumor or metastasis), not be evaluated as described in the protocol due to missing pre-biopsy samples.

As the technology used by [REDACTED] eliminates much more the subjective measurement of CD8+ infiltration and has been technically validated, the [REDACTED] approach is widely regarded as the more accepted one in contrast to the [REDACTED] approach. Additionally, issues in the quality of the execution had been identified in the beginning of the

[REDACTED]

[REDACTED]

[REDACTED]

Evaluation of auto- and allo-immunization parameters

Auto- and alloimmunization parameters will be assessed prior to vaccination at Vacc1 Visit and at Sun-Start Visit for patients randomized to Intuvax.

Autoimmunization parameters, anti-nuclear antibodies (IF-ANA), anti-mitochondrial and anti-liver-kidney icrosomal antigens will be assessed as “Negative” or “Positive” and additional assessment of “Weak” or “Strong” will be done for positive results on Homogenous, Speckled, Nucleolar, and Centromere patterns.

Alloimmunization at the humoral level by screening of alloantibodies against HLA-A, B, C (HLA class I) and HLADR, DQ, DP (HLA class II) antigens will be assessed as “Present” or “Not Present”.

The results of auto- and allo-immunization parameters will be tabulated using general summary statistics for categorical data. In addition shift tables will be presented to summarise the changes from the assessment prior to vaccination 1, to the Sun-start visit.

TTF defined as progressing during or after treatment with Intuvax+sunitinib or sunitinib followed by the start of subsequent second line systemic therapy

TTF is defined as progressing during or after treatment with Sunitinib or Intuvax + Sunitinib followed by the start of subsequent second line systemic therapy including immune checkpoint inhibition or tyrosine kinase inhibition, and will be derived as the date of screening until start date of second line treatment following progression. Similar censoring rules as applied for PFS will be used. Patients with PD without any second line treatment will be censored at withdrawal. Similar survival statistics as applied for analysis of PFS will be conducted.

Association between Sunitinib dose density and primary and secondary endpoints

Exploratory analyses will be conducted where the influence of individual Sunitinib dose density on the outcome of primary and secondary endpoints will be evaluated. This will be done by applying a cox regression overall, including treatment group, strata and average dose density during the time leading up to either event or censoring. Initially a treatment group by dose density interaction will be included, if the interaction term is not significant the interaction will be dropped from the model.

Sunitinib dose density will be derived as the total recorded dose during the time leading to event or censoring divided by the corresponding time period.

These analyses will be conducted for evaluation of primary endpoint and PFS and in addition summary statistics for dose density will be provided split by treatment group and best response rate, ORR and DCR.

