3.2 Definition of Terms

NB: Detailed definitions of terms from the updated guideline Response Evaluation Criteria In Solid Tumors (RECIST v1.1) [1] are included in *Section 10.2.2.2* and detailed definitions for Dose Limiting Toxicity (DLT) based on Common Terminology Criteria for Adverse Events (CTCAE) grading [2] for specific AEs are presented in *Section 11.5*.

Baseline	
The date of randomization is defined as baseline for OS and 18-month survival rate.
 
The centrally assessed CT performed at the Sunitinib Start Visit is defined as CT baseline for evaluation of PFS, response rate and time to progression (TTP) after start of sunitinib in intermediate- and high-risk patients, Section 10.2.2.1, Section 10.2.2.2, and Section 10.2.2.3. Note: For intermediate-risk patients included in the trial according to protocol versions before version Final 4.0, baseline for PFS, ORR and duration of response, and TTP is defined as the first imaging assessment after nephrectomy.
 
The Screening Visit is defined as baseline for all other assessments than those listed above.

Competent Authority (CA)	A government body or government appointed body that has legal authority to approve or disapprove clinical studies
Eastern Cooperative Oncology Group (ECOG) criteria (also referred to as WHO or Zubrod) [3]	
0 Fully active, able to carry on all pre-disease performance without restriction
 
1 Restricted in physically strenuous activity but ambulatory and able to carry out work of a light or sedentary nature, e.g., light house work, office work
 
2 Ambulatory and capable of all self-care but unable to carry out any work activities. Up and about more than 50% of waking hours
 
3 Capable of only limited self-care, confined to bed or chair more than 50% of waking hours
 
4 Completely disabled. Cannot carry on any self-care. Totally confined to bed or chair
 
5 Dead

High-risk mRCC patient according to Heng criteria [4]	
Patients fulfilling three (3) to six (6) of the following prognostic factors:
 
 • Hemoglobin (Hb) less than the lower limit of normal (LLN) • Corrected Calcium (Ca) greater than upper limit of normal (ULN) • Karnofsky performance status less than 80% • Time for diagnosis to treatment less than one (1) year • Neutrophils greater than ULN • Platelets greater than ULN

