10.2.2 Secondary Efficacy Variables and Assessments

10.2.2.1 Progression Free Survival (PFS) from Start of Sunitinib

PFS from start of sunitinib is defined as time from Sunitinib Start Visit to PD or death following sunitinib initiation from any cause, whichever occurred first. PFS from start of sunitinib will be evaluated per stratum and in total from the two (2) different treatment arms as a secondary efficacy variable.

Note: For intermediate-risk patients included in the trial according to protocol versions before version Final 4.0, sunitinib treatment did not have to be initiated at a fixed time point. For these patients, the first imaging assessment after nephrectomy will be used as baseline for evaluation of PFS, irrespective of whether or not the imaging assessment coincided with sunitinib treatment start. Further details will be provided in the Statistical Analysis Plan (SAP).

10.2.2.2 Objective Response Rate and Duration of Response and Stable Disease from Start of Sunitinib

Evaluation of tumor response is based on centrally assessed CT scans, *Section 10.4.3*, according to the RECIST 1.1 guideline [1].

Definitions - RECIST v1.1

a) Measurable Disease

The presence of at least one (1) measurable lesion. If the measurable disease is restricted to a solitary lesion, its neoplastic nature should be confirmed by cytology/histology. The same measurable and non-measurable lesions will be followed by RECIST v1.1. Disease progression will be determined using RECIST v1.1 criteria.

- Malignant lymph nodes

To be considered pathologically enlarged and measurable, a lymph node must be >15 mm in short axis when assessed by CT scan (CT scan slice thickness

recommended to be no greater than 5 mm). At baseline and in follow-up, only the short axis will be measured and followed.

- **Baseline documentation of “Target” and “Non-Target” lesions**
All measurable lesions up to a maximum of 2 lesions per organ and 5 lesions in total, representative of all involved organs, should be identified as target lesions and recorded and measured at baseline.

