
Incomplete Response/ Stable Disease (SD)	Persistence of one or more non-target lesion(s) or/and maintenance of tumor marker level above the normal limits
------------------------------------------	------------------------------------------------------------------------------------------------------------------

^a Although a clear progression of “non-target” lesions only is exceptional, the opinion of the treating physician should prevail in such circumstances, and the progression status should be confirmed at a later time by the Investigator.

Evaluation of Best Overall Response

The best overall response is the best response recorded from the start of the treatment Sunitinib until disease progression/recurrence (taking as reference for PD the smallest measurements recorded since the treatment started). In general, the subject's best response assignment will depend on the achievement of the measurement criteria.

Table 6 Evaluation of Best Overall Response

Target Lesions	Non-Target Lesions	New Lesion	Overall response
CR	CR	No	CR
CR	Incomplete response/SD	No	PR
PR	Non-PD	No	PR
SD	Non-PD	No	SD
PD	Any	Yes or No	PD
Any	PD	Yes or No	PD
Any	Any	Yes	PD

Subjects with a global deterioration of health status requiring discontinuation of treatment without objective evidence of disease progression at that time should be classified as having “symptomatic deterioration.” Every effort should be made to document the objective progression even after discontinuation of treatment.

Note: For intermediate-risk patients included in the trial according to protocol versions before version Final 4.0, the first imaging assessment after nephrectomy will be used as baseline for evaluation of best overall response, irrespective of whether or not the imaging assessment coincided with sunitinib treatment start. Further details will be provided in the SAP.

Definitions for Response Evaluation

a) Confirmation of Response

To be assigned a status of complete or partial response, changes in tumor measurements do not need to be confirmed by repeat assessments after the criteria for response are first met.

b) Response rate

To be evaluated as the highest observed score of response during the study after randomisation in the ordinal categories of CR, PR, PD, SD and “Not evaluable”. The response rate will be evaluated according to the Schedule of Study Events, *Section 7.2.1*.

c) Objective response

Is defined as the proportion of patients with CR and PR.

d) Disease control rate (DCR)

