10.2.2.3 Time to Progression (TTP) from Start of Sunitinib

TTP defined as time from Sunitinib Start Visit to date of first observed progression or date of death if the death was due to disease progression (whichever came first). Progressive disease is defined by RECIST v1.1 criteria and by clinical evaluation.

Note: For intermediate-risk patients included in the trial according to protocol versions before version Final 4.0, the first imaging assessment after nephrectomy will be used as baseline for evaluation of TTP, irrespective of whether or not the imaging assessment coincided with sunitinib treatment start. Further details will be provided in the SAP.

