12.1.6 Secondary Efficacy Analyses

Secondary efficacy endpoints will be presented descriptively by stratum (High-/Intermediate-risk mRCC patients) as stated explicitly for each endpoint below. Further analyses may be defined in the SAP, if appropriate. All secondary endpoints will be evaluated using the FAS. In addition, the PPS will be used.

PFS from start of sunitinib in intermediate and high-risk mRCC patients

The PFS analysis will be based on the subgroup of patients from FAS that actually had been exposed to at least one dose of sunitinib. PFS will be evaluated using similar survival statistics as described for the analysis of the primary endpoint.

Note: For intermediate-risk patients included in the trial according to protocol versions before version Final 4.0, sunitinib treatment did not have to be initiated at a fixed time point. For these patients, the first imaging assessment after nephrectomy will be used as baseline for evaluation of PFS, irrespective of whether or not the imaging assessment coincided with sunitinib treatment start. Further details will be provided in the SAP.

All other secondary endpoints defined as a time-to-event endpoint will be analyzed using the same statistical approach.

Response rate from Sunitinib Start Visit

Evaluation of response rate, based on CT and according to the RECIST 1.1 guideline, from Sunitinib Start Visit will be based on the subpopulation from FAS who have been exposed to at least one dose of sunitinib. Number of patients with CR, PR, PD, and SD after start of sunitinib will be summarized as described in *Section 12.1.4* for categorical data, using the underlying ordinal scale.

ORR including DCR will be summarized descriptively. Waterfall charts will be used to display the response distribution, details for this will be provided in the SAP. Between group comparison of the proportions will be done using Cochran Mantel Haenzel test including stratum on high-risk and intermediate-risk groups as a fixed factor.

Note: For intermediate-risk patients included in the trial according to protocol versions before version Final 4.0, the first imaging assessment after nephrectomy will be used as baseline for evaluation of ORR, irrespective of whether or not the imaging assessment coincided with sunitinib treatment start. Further details will be provided in the SAP.

Number of infiltrating CD8+ T-cells

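### For intermediate-risk patients included before protocol version 4.0, the SAP's PFS/TTP origin, PFS population and CT baseline do not match the rules the protocol fixes for them

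*SAP*

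**What the plan says.** The patients in question are intermediate-risk patients included under protocol versions before 4.0 (below, pre-4.0 patients). SAP 4.1 explains that, under that design, they were to begin sunitinib only once progression had been confirmed.

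**Protocol.** Section 3.2 states that for these patients "baseline for PFS, ORR and duration of response, and TTP is defined as the first imaging assessment after nephrectomy". Section 10.2.2.1 repeats the rule for PFS and adds that it holds "irrespective of whether or not the imaging assessment coincided with sunitinib treatment start". Section 10.2.2.3 says that "the first imaging assessment after nephrectomy will be used as baseline for evaluation of TTP", and section 10.2.2.2 that "the first imaging assessment after nephrectomy will be used as baseline for evaluation of best overall response". Section 12.1.6 restates it for the analysis: "For these patients, the first imaging assessment after nephrectomy will be used as baseline for evaluation of PFS" and "the first imaging assessment after nephrectomy will be used as baseline for evaluation of ORR". These statements cover the whole pre-4.0 group. Sections 10.2.2.1 to 10.2.2.3 and 12.1.6 leave further details to the SAP. Section 12.1.6 also sets the PFS population as the "subgroup of patients from FAS that actually had been exposed to at least one dose of sunitinib".

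**SAP.** Section 6.3.6 measures PFS from the sunitinib start date by default. Its special rule is that "patients who either had a delay or never started sunitinib will be included under the assumption that sunitinib treatment would have been initiated" as in the final design, with the date of the next visit after nephrectomy as origin. TTP is derived in the same way. Section 5 allows pre-4.0 patients into the sunitinib-based endpoints on the terms described for PFS. Section 6.3.1 names the CT at the Sunitinib Start Visit as baseline for PFS, response rate and TTP, with no pre-4.0 note. The response-rate text in 6.3.6 is limited to dosed patients and has no such note either.

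**The concern.** The protocol leaves detail to the SAP, but it fixes the baseline itself. The SAP then states a different one, for a differently defined set of patients. Two programmers, each following one document, could time the same patient from different dates or assess the same patient against different reference scans.

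The word *delay* makes this worse. It has no definition, and under the pre-4.0 design the timing of sunitinib followed the timing of progression. Whether a patient counts as delayed is therefore tied to outcome. SAP 6.2 acknowledges that data review in this open-label trial is not blind, so the classification could be settled with outcomes in view. PFS and TTP are compared by stratified log-rank test and again within each stratum, and all the affected patients sit in the intermediate-risk stratum.

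**Working it through.** The plan gives no figure for this point, so there is none to reproduce. The check compares the rules and then does the date arithmetic.

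**Step 1. Rules for pre-4.0 patients**

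| Item | Protocol | SAP |
|---|---|---|
| PFS origin | First scan after nephrectomy (3.2, 10.2.2.1, 12.1.6) | Next visit after nephrectomy if delayed or never started; otherwise sunitinib start (6.3.6) |
| TTP origin | First scan after nephrectomy (3.2, 10.2.2.3) | As for PFS (6.3.6) |
| Patients given the special origin | All pre-4.0 | Only delayed (undefined) or never started |
| PFS population | At least one sunitinib dose (12.1.6) | Never-started patients included (5, 6.3.6) |
| CT baseline for PFS, TTP and response | First scan after nephrectomy (3.2, 10.2.2.2, 12.1.6) | Sunitinib Start Visit CT, no exception (6.3.1) |

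The origin differs in both the date used and the patients covered. The PFS population differs. The CT baseline differs by omission.

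**Step 2. How far apart can visit and scan be?** Inputs: protocol 7.2.1.5 puts the Sun-Start Visit 5 to 8 weeks after nephrectomy, and lets its CT fall on another day within that window. The pre-4.0 visit schedule is not in the documents, so using this window is an assumption.

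Maximum gap = (8 − 5) × 7 = 21 days, in either direction.

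**Step 3. One patient under each rule.** Formula (SAP 6.3.6): event date minus origin date plus 1. Days are counted from nephrectomy, and all are assumed. First progression is on day 119.

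- Scan day 35, visit day 56: protocol 119 − 35 + 1 = 85 days; SAP visit rule 119 − 56 + 1 = 64 days.
- Scan day 56, visit day 35: protocol 119 − 56 + 1 = 64 days; SAP visit rule 119 − 35 + 1 = 85 days.
- Scan and visit both day 49: 119 − 49 + 1 = 71 days under both.

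The difference can go either way and disappears when scan and visit coincide.

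**Step 4. Scale.** No median PFS is given. For assumed medians of 6, 9 and 12 months (30.4375 days per month), 21 days is 21/182.6 = 11.5%, 21/273.9 = 7.7% and 21/365.25 = 5.7%. This is the largest shift for one patient, not an effect on the trial estimate, which would also need the number of pre-4.0 patients and their actual dates.

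**The case against.** The case for leaving the SAP alone has some force. If SAP 4.1 describes what happened, nearly every pre-4.0 patient was delayed or never started, so the special rule reaches almost the group the protocol names. In the current schedule the next visit after nephrectomy is the Sun-Start Visit, where the CT is also planned, so scan and visit may be nearly the same event. The central imaging protocol, which is not among the documents, may already fix the reference scan. The endpoints are exploratory and the trial is not powered.

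These arguments limit the size of the problem but do not remove it. Permission to add detail does not extend to replacing a rule the protocol states, and a rule that covers almost everyone still needs a definition for the rest.

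Some stronger readings are tempting but unsupported:

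- *The SAP uses a visit date as the response baseline.* It does not. It keeps the Sunitinib Start Visit CT and omits the exception.
- *Some patients would get zero or negative PFS times*, because progression preceded sunitinib. This requires a patient not classed as delayed whose progression is counted against a scan other than the baseline SAP 6.3.1 names.
- *The two baselines give different partial-response thresholds of a known size.* This assumes the progression scan serves as the Sunitinib Start CT, although SAP 6.3.1 could equally mean the scan at 5 to 8 weeks. It also ignores that protocol 10.2.2.2 counts best response only up to progression.
- *The SAP failed to record the changes.* Two bullets of SAP 6.1 are redacted, so this cannot be known.
- *Pooling these patients with the rest is itself a departure.* The protocol pools them too.

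**Conclusion.** The conflict is real in three respects: the origin for PFS and TTP, the PFS population, and the CT baseline for PFS, TTP, best overall response/ORR and duration of response. It should be resolved before analysis.

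Its reach is limited. OS, 18-month survival and PFS within the high-risk stratum are untouched. What is affected is the intermediate-risk stratum and the pooled analysis of secondary, exploratory endpoints. For most pre-4.0 patients the origin question probably reduces to visit date against scan date, with the 21-day ceiling resting on the assumption that the current window applied to them. Patients on the border of the undefined delay are where the choice of origin is most open. The rule is the same in both arms, and nothing in the documents shows which arm, if either, would gain. Since the number of pre-4.0 patients is not given, no effect on the trial result can be stated.

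**What to change.** 1. In SAP 6.3.6, use the date of the first imaging after nephrectomy as PFS and TTP origin, and that scan as RECIST reference, for every pre-4.0 intermediate-risk patient. Delete the delay condition.
2. Carry the same exception into SAP 6.3.1 and the ORR, duration-of-response and TTP text.
3. Reconcile the inclusion of never-started patients in SAP 5 and 6.3.6 with the dosed population in protocol 12.1.6, and say whether it applies to TTP and response as well. Make sure SAP 6.1 records the outcome, if a redacted bullet does not already do so.
4. Optionally, keep the pooled analysis as main and add a pre-specified sensitivity analysis of PFS and TTP without pre-4.0 patients, overall and in the intermediate-risk stratum. Neither document requires it, but it would show the result under the final design.

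Items 1 to 3 cost SAP wording, one reconciling sentence and one check of SAP 6.1. Item 4 costs one or two tables, with fewer patients and wider intervals in the restricted analysis.
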